# **REVISION HISTORY**

Revision #	Version Date	Summary of Changes	Consent Change?
1.2	31 January	Amended the title to include	No
	2020	"Short-term"	
2	14 August 2020	
 
Substituted the original stationary, wired laryngeal vibration device with a wearable, wireless device.
 
Shortened the procedure. Instead of 3x17 min vibration, participants will only receive 2x20 min vibro- tactile stimulation.
 
An option for remote testing was added to the protocol.
 
	Yes
3	24 August 2020	Responded	
4	14 October 2020	Responded	Remote testing consent added.
5	31 January 2021	1- Added usability testing questionnaire to the protocol	Yes

Page 2 of 27

PROTOCOL TITLE:	Effect of Short-term Laryngeal Vibration on Voice Quality. Grant
	title: Feasibility of laryngeal vibration as a treatment for
	spasmodic dysphonia
VERSION DATE:	01/31/2021

### **ABBREVIATIONS/DEFINITIONS**

- EEG: Electroencephalogram
- FD Focal dystonia
- SD: Spasmodic dysphonia
- VTS: Vibro-tactile stimulation

Page 4 of 27

PROTOCOL TITLE:	Effect of Short-term Laryngeal Vibration on Voice Quality. Grant
	title: Feasibility of laryngeal vibration as a treatment for
	spasmodic dysphonia
VERSION DATE:	01/31/2021

# **STUDY SUMMARY**

Study Title	Effect of Laryngeal Vibration on Voice Quality
Study Design	Single-intervention, pre- posttest design. Subjects
	perform voice production tasks before, during and
	after vibration.
Primary Objective	The purpose of this research is to examine the
	effects of laryngeal vibration on objective markers
	of speech quality in healthy human volunteers and
	people with spasmodic dysphonia, a voice disorder
	affecting the laryngeal muscles.
Secondary Objective(s)	Obtain preliminary data in a limited sample of SD
	patients that show the potential effectiveness of the
	approach after a single application of vibro-tactile
	stimulation (VTS) of the larynx.
Research	Vibro-tactile stimulation of the superficial skin
Intervention(s)/Investigational	surface above the larynx (human voice box)
Agents	
Scientific Assessment	Nationally based non-federal funding organizations-
	National Spasmodic Dysphonia Association
IND/IDE # (if applicable)	NSR IDE
IND/IDE Holder	N/A
Investigational Drug Services	N/A
# (if applicable)	
Study Population	People diagnosed with spasmodic dysphonia and
-	healthy adult volunteers without a voice disorder
Local Sample Size (number of	We have recruited 17 – 9 females, 6 males (as of
participants recruited locally)	6/5/2018)

Page 5 of 27

#### 1.0 Objectives

#### 1.1 Purpose:

The general aim of the research is to provide scientific evidence that VTS represents a non-invasive form of neuromodulation that can induce measurable improvements in the speech of SD patients. This research addresses a clinical need to develop alternative or auxiliary treatments for a rare voice disorder with limited treatment options. A successful completion of the proposed work will be an important step in advancing laryngeal VTS as a therapeutic intervention for improving the voice symptoms in SD. Specifically, the scientific yield by achieving the specific aims is threefold: First, it will elucidate the unknown neurophysiological mechanism behind laryngeal VTS by documenting the neural changes associated with VTS. Second, it will establish that VTS can improve voice quality in SD. Third, by documenting that laryngeal VTS yields long-term benefits on voice quality in SD patients, it would provide a solid basis for a clinical trial that needs to address open questions on optimal dosage and duration of VTSbased voice therapy, the magnitude of the therapeutic effect across adductor and abductor SD and its long term efficacy.

#### 2.0 Background

2.1 Significance of Research Question/Purpose:

The general aim of the study is to provide preliminary scientific evidence that VTS represents a non-invasive form of neuromodulation that can induce measurable improvements in the speech of SD patients. This work addresses a clinical need to develop alternative or auxiliary treatments for a rare voice disorder with very limited treatment options. A successful completion of the proposed work will be an important step in advancing laryngeal VTS as a therapeutic intervention for improving the voice symptoms in SD.

2.2 Preliminary Data:

We conducted a series of preliminary investigations to assess the feasibility of applying VTS to the human larynx. First, we searched for suitable vibrators that could be applied to the skin above the voice box and provide the necessary amplitude to penetrate sufficiently the thyroid cartilage and to stimulate the underlying mucosal mechanoreceptors and/or proprioceptors of extrinsic laryngeal muscles. Second, we recorded the acoustic signals during vocalization with and without VTS to determine its effect on voice production. Third, we measured the EEG responses to laryngeal vibration to understand the cortical responses to laryngeal VTS.

Selecting and piloting appropriate vibrators. We systematically tested a range of commercially available, small precision vibrators that delivered

Page 6 of 27

amplitudes between 1.7-14.3 G (based on 100g inertial load testing). Vibrators were attached to the skin above the larynx of healthy volunteers and tested under varying voltage inputs. During testing subjects repeatedly vocalized vowel tones for 6-second intervals that were recorded for later acoustic frequency analysis. It became clear that vibrators with amplitudes above 6G are unsuitable (e.g. induced a gag reflex at higher voltage; uncomfortable to wear for prolonged periods of time (> 10 min). We systematically narrowed the selection to a encapsulated cylinder vibrator (Fig. 1) that has a maximum amplitude < 6G and produced clearly detectable periodic signals in the acoustic data at frequencies that were within the frequency range known to stimulate laryngeal mechanoreceptors [1].

#### Existing Literature:

SD is a characterized by involuntary, random movement of laryngeal muscles causing disruption of fluent speech with strained-strangled voice quality. SD is more prevalent in women [2, 3]. Onset is typically in midlife. There are two types of SD: (a) adductor (AD) typified by uncontrolled vocal fold closure, and (b) abductor (AB) characterized by uncontrolled vocal fold opening. The AD form is more common and typically occurs during the voiced components of speech. SD symptoms are task specific, occurring during speech but not during other phonatory (e.g., prolonging vowels) or non-phonatory tasks (e.g., breathing). SD shares several abnormal neurologic signs with FD of the head, neck and hand. For example, abnormal blink reflexes were observed in SD, torticollis, and blepharospasm [4-7] and abnormal long-latency responses to peripheral nerve stimulation have been observed in SD [8], in blepharospasm and oromandibular dystonia [9]. Recent evidence from our group and the work of others strongly indicate that basal ganglia-related diseases such as Parkinson's disease or certain forms of dystonia are associated with somatosensory and specifically proprioceptive abnormalities that are closely linked to the observed motor deficits [10-21] (for reviews see: [22, 23]). Finally, our own work confirmed that SD as a voice disorder is associated with a deficit in arm kinaesthesia [24] – a finding consistent with results from patients with FD of the head and neck [21].

Neurophysiology behind VTS. It has long been established that VTS can stimulate muscle spindles [25-27] and mechanoreceptors [28] affecting motor behavior and inducing changes in kinaesthesia [29-31]. In general, vibrating the skin at amplitudes of  $\leq 15 \,\mu\text{m}$  is sufficient to activate Ia muscle spindle afferents of superficial muscles, which evokes a contractile response called the Tonic Vibration Reflex [26, 27]. To elicit kinaesthetic illusions, vibration must typically range between 40-100 Hz [32, 33]. Brief vibration to a relaxed muscle typically leads to an increase in muscle tone that can easily be overcome by voluntary phasic innervation [34], while

Page 7 of 27

excitatory input to spinal  $\alpha$ -motor neurons is depressed when vibration is applied for prolonged periods [35]. At the cortical level it has been shown that prolonged muscle tendon vibration of wrist flexors (30 min) induced an increase in corticospinal excitability of the antagonistic wrist extensors lasting up to 60 min after vibration indicating that VTS can induce measurable changes in short-term cortical plasticity [36, 37].

Somatosensory deficits and VTS in FD. Numerous research reports documented somatosensory deficits in FD (for review see [38]). For example, proprioceptive-based finger position sense thresholds and the perception of arm motion are abnormal in patients with cervical dystonia or blepharospasm [21, 39]. The abnormalities in tactile and proprioceptive processing are not restricted to the affected dystonic musculature, but were also documented in non-affected body regions [21, 40, 41] indicating a generalized somatosensory deficit in FD. Recording of somatosensory evoked potentials (SEPs) and TMS data document that abnormal processing of somatosensory information in FD is associated with abnormally enhanced cortical excitability and decreased intracortical inhibition [42, 43], which also has been confirmed for SD [44]. The susceptibility of FD to somatosensory stimulation has long been known, because patients with taskspecific dystonia may use sensory tricks (geste antagoniste) to temporarily alleviate dystonic symptoms by touching or pressing areas of or near the dystonic musculature [45, 46]. Research on cervical dystonia documented that effective sensory tricks are associated with pallidal and motor cortical desynchronization at low frequencies (6-8Hz) [47]. It has further been shown that FD responds to VTS. Vibrating dystonic neck muscles of patients with torticollis, who exhibit abnormally tilted head postures, induced head righting and nearly restored normal head posture [48]. Vibrating non-dystonic arm muscles in patients with cervical dystonia and blepharospasm skewed arm position sense to a greater extent than healthy controls [39]. In summary, there is overwhelming evidence that somatosensory processing is affected in many forms of FD (for reviews see [22, 38]). VTS has been shown to influence somatosensory perception and may reduce the severity of dystonic postures [13, 39, 45, 48].

One challenge in applying VTS to the speech motor system is that intrinsic laryngeal muscles and the mucosa of the epiglottis are shielded by thyroid cartilage. While proprioceptors of limb muscles can be stimulated by placing vibrators on the skin above them, this is not possible for laryngeal muscles. That is, non-invasive vibrators are needed that can be easily attached to the skin above the larynx and vibrate with sufficient amplitude to induce responses in laryngeal mechanoreceptors. Many of the vibrators that have been used in the past to investigate vibration responses in limb muscles are not suitable due to size, weight and voltage requirements. Fortunately, recent advancements in vibrator technology (largely driven by cell phone

Page 8 of 27

engineering) have produced small, low voltage, yet powerful vibrators that, for the first time, make it feasible to wear and operate vibrators at the neck for a prolonged time without restricting a person's movement.

#### 3.0 Study Endpoints/Events/Outcomes

3.1 Primary Endpoint/Event/Outcome:

If successful, the work under this protocol would lay the scientific foundation for a clinical trial to examine the usefulness of the approach in a larger patent sample. It would document the sensorimotor cortical activation patterns associated with SD and the cortical responses to VTS. It would promote development of wearable, user-programmable medical devices that could apply VTS while monitoring its effect on voice production in realtime. Ultimately, VTS would enlarge the available therapeutic arsenal by either augmenting existing Botox therapy or becoming an alternative intervention option for patients who do not tolerate Botox injections.

#### 4.0 Study Intervention(s)/Investigational Agent(s)

#### 4.1 Description:

The participants will wear a light-weight, wearable collar (See figure 1) that can be removed as easy as a bracelet. The complete system consists of two components: 1) a flexible enclosure that houses the electronics, 2) a collar made of soft, wear-resistive, and washable textile materials. The collar has a pouch, in which the electronics enclosure can be inserted. The enclosure can be removed from the textile collar for separate cleaning of the collar after prolonged wear, which is every single testing session.

The output of the microphone or accelerometer embedded in the device will be stored locally in the wearable device for automatic internal processing in the wearable device to activate the vibrators or calculate the threshold using the developed algorithms. The stored data will be automatically removed every 60 s and data will be never transferred out of the wearable device. In the control mode, either the voice or the accelerometer data will be used by the device to activate the vibrators when the user vocalizes or speaks. We have implemented a detection algorithm that uses either the accelerometer signal or the acoustic signal from the microphone to turn the vibrators on and off.

Page 9 of 27

*Figure 1*: Schematic illustration of a laryngeal vibration device having vibrators carried by a collar.

Figure 2. Vibratory motor used for this study (Precision Microdrives Ltd., London, UK, Model 307 – 100) Length: 25 mm. Diameter: 9 mm.

The device applies vibration to the to the skin above the larynx using two vibratory motors. The vibratory motors (Precision MicrodrivesTM, Model 307 - 100) used are low-voltage (~1V) and non-invasive. For this protocol, they vibrate at frequencies between 30 - 100 Hz (i.e. 100 times per second). The small electric motors are encapsulated (see **Fig. 2**). There are no moving parts that can come in contact with the skin. At a stimulation frequency of 100Hz, the inertial load is approximately 2.7G, which translates to a vibration amplitude well below the threshold that may induce a swallowing reflex (> 6G). The vibrators embedded in the device are movable, thus we are able to position them around the larynx of every participant. The microphone embedded in the device is positioned in front of the larynx. Prior to testing, the microphone of the wearable device will record the audio signal used to determine a signal power threshold to adjust the signal-to-noise ratio of the voice signal. These recorded data will not be transferred from the wearable device, but are deleted from device memory as soon as the threshold calculation is

Page 10 of 27

completed. The process of calculating threshold is automatic and does not require interaction by the user or the experimenter.

Using the calculated threshold, the speech detection algorithm will turn on the vibrators. To ensure consistency across all participants, the vibration frequency will be held constant at 100Hz for all participants.

The rotating mass of each vibrator in of the device is encapsulated. It does not come in direct contact with the skin. The position of vibrators relative to the voice box can be adjusted. The vibrators need to be placed around the larynx (Figure 3). For inperson testing, the study personnel will manually adjust the location of the device vibrators according to the width of the larynx of the participant. For remote session testing, the participant will measure the width of his/her larynx during the video call with study personnel. Next, the participant will be instructed to move the vibrators and place them apart to the value of measured larynx width from the previous step. Finally, the participant will wear the wearable device in front of the camera. The study personnel via video call will check and make sure the placement is consistent with the study protocol.

The device has a physical on/off switch that the user controls. No tablet or computer is necessary for operation. Participants will download an app to their smart phones. That app will allow users 1) to turn the vibratory motors on or off remotely (i.e. without the use of the physical switch), 2) to change to mode of operation to continuous vibration for a specified time between 1-20 min, ), or 3) to turn on the voice detection mode, during which VTS will only be turned on during detected speech. The vibration frequency cannot be altered by the user. A resistor embedded in the electronics controls the output voltage to 1.1 V, which corresponds to a 100Hz vibration.

#### 4.2 Drug/Device Handling:

The strength of the vibration is similar to the vibration experienced from vibrating cell phones or gaming joysticks. Vibro-tactile stimulation at the applied frequency and amplitude is not known to cause pain or tissue damage. The participant may feel a mild tingling or vibrating sensation. Preliminary testing on healthy human subjects showed that at the given vibration parameters (see 4.1) no adverse reactions occur.

Page 11 of 27

*Figure 3.* Demonstrating the placement of vibratory motors on the larynx. During this study, the vibrators are embedded in the wearable collar.

#### 5.0 Procedures Involved

#### 5.1 Study Design:

Subjects will perform voice production tasks before, during and after vibration. The subject will wear the collar around their neck. Two lightweight, low voltage, non-invasive surface electrical vibratory motors that are embedded in the wearable collar will be positioned on the skin of the anterior portion of the neck adjacent to the voice box to vibrate the larynx (see Fig. 3 for demonstrating the location of vibrators). Voice production before, during, and after the vibration will be recorded via a microphone for subsequent acoustic analysis on voice quality by speech analysis experts. In addition, during voice production, electroencephalography (EEG) will be recorded with a 64-channel system (Active 2 BioSemi B.V., Amsterdam, The Netherlands or the mobile ANT Neuro EEGO EEG System, Hengelo, The Netherlands) at a sampling frequency of 512 Hz. Subjects will wear a regular head cap arranged in the standard 10-20 configuration (see Figure 1). Four additional external electrodes will be used. Two electrodes will be placed above and below the left eye to detect eye movements. Another two electrodes will be attached on bilateral mastoid processes to serve as reference electrodes. A water-based conductive gel is applied between the electrodes and the skin, which can be cleaned easily with water.

Deleted: Figure 1

Page 12 of 27

#### PROTOCOL TITLE: Effect of Short-term Laryngeal Vibration on Voice Quality. Grant title: Feasibility of laryngeal vibration as a treatment for spasmodic dysphonia 01/31/2021

VERSION DATE:

Figure 1 EEG cap with 10-20 electrode configuration

#### 5.2 Study Procedures:

Voice assessment. To assess voice quality, participants will perform two voice production tasks. First, they will vocalize the vowels 'ahh' and 'ee'. They will perform each task three times per assessment. Second, they read aloud twenty test sentences. They will repeat these assessments several times during testing (see Fig. 4). The sentence reading task consists of a set of test sentences based on a 20-sentence inventory described by Ludlow et al. as being sensitive to the voice symptoms experienced in SD [2]. Participants will read the sentences at their own comfortable pace and loudness. In addition, participants will rate their perceived effort level of vocalization on an ordinal scale of 0 to 10 (0 being with no effort and 10 being with maximal effort).

Application of laryngeal vibration. Each VTS trial begins with a 10-second rest period, followed by 4 seconds of vocalization. After 2 seconds of vocalization, vibration will set in while the subject continues to vocalize. Thus, each trial has a rest, a vocalization only, and a vocalization + vibration period. Each participant performs 50 trials per set. The timeline of the complete protocol is illustrated in Figure 4. Testing will begin with a pretest voice assessment, followed by two sets comprising the vibration only and vocalization + vibration conditions. The order of the conditions will be counter-balanced between subjects to account for possible order effects. During the vibration only condition, subjects will be silent and are allowed to read for diversion. After each set a 5-min break will be given and fluids will be offered. Voice assessment batteries will be administered after each set. After completion of two sets and final voice assessments are immediately after treatment (Post 2 OFF), and 20 min and 60 min after VTS has stopped (Post 20, Post 60).

Page 13 of 27

Revised: 9/28/2017

#### Deleted: 4

PROTOCOL TITLE: Effect of Short-term Laryngeal Vibration on Voice Quality. Grant title: Feasibility of laryngeal vibration as a treatment for spasmodic dysphonia 01/31/2021

Figure 2 Experimental design for in-person testing.

Usability questionnaire: The last section of study is to ask participants to fill out a questionnaire about the usability of the wearable collar.

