#### 15.0 Statistical Considerations

#### 15.1 Data Analysis Plan:

Analysis of voice data. Acoustic analysis will follow the methodology described by [50]. Waveform and wide-band spectrograms will be used to identify and measure the duration of the variables. The acoustic signal will be examined for the presence of phonatory breaks and aperiodic breaks. Phonatory breaks are defined as any voiced phonemic segment without sound that is greater than 50ms; the duration of phonatory breaks will be measured. Aperiodic segments will be identified as any voiced phonemic segment that contains non-repetitive cycles that are greater than 50ms; and the duration of the break will be measured. To standardize the duration measures for both phonatory and aperiodic breaks, the sum of the duration of breaks will be divided by the sum of the duration of all voiced segments for each subject. Inter-rater reliability will be measured using Cohen's alpha and intra-rater reliability will use Pearson's r correlation (expected to range between r=.89 to r= .98 according to [50]). For both break types, the absence of phonation or the presence of aperiodicity at the boundary of a syllable or the beginning of a word will not be considered. We will perform a MANCOVA procedure employing all acoustic variables with pre-/posttests as independent factors. If the MANCOVA is significant, separate univariate ANOVAs will be performed on each acoustic variable (dependent) and assessment conditions as a repeated measure (independent) [50]. Appropriate Bonferroni adjustments will account for multiple testing.

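### Set order is counterbalanced, but the voice model names no set-condition, order or order × assessment term, which costs precision and probably the contrast between the two sets

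*Combined protocol and SAP*

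**What the plan says.** Section 5.2 (Study Procedures) opens testing with a pretest voice assessment, "followed by two sets comprising the vibration only and vocalization + vibration conditions". It then states: "The order of the conditions will be counter-balanced between subjects to account for possible order effects". Voice is measured around both sets: "Voice assessment batteries will be administered after each set", and the "final voice assessments are immediately after treatment (Post 2 OFF), and 20 min and 60 min after VTS has stopped (Post 20, Post 60"). The gap between sets is short: "After each set a 5-min break will be given and fluids will be offered".

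Section 15.1 (Data Analysis Plan) is the only plan for the voice data. Its multivariate step reads "We will perform a MANCOVA procedure employing all acoustic variables with pre-/posttests as independent factors". The follow-up ANOVAs take each acoustic variable in turn, with "assessment conditions as a repeated measure (independent") as the only named factor. That factor is not defined. No order, order × assessment or set-condition term is named, and the MANCOVA names no covariate.

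**The concern.** Section 5.2 builds a two-condition crossover into one session and counterbalances it, and section 15.1 then makes no use of that structure. The single repeated factor can be read in two ways, and each leaves out one of the two things the crossover varies.

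- **Time points.** The assessment after set 1 averages people who sat silent during vibration with people who vocalized during it. The difference between them has no term in the model.
- **Set condition.** The difference has a term, but whether a set came first or second does not.

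At stake is whether the study can say that voice changed differently after the two ways of applying vibration, and how much avoidable noise enters a comparison based on 20 patients and already subject to Bonferroni adjustment.

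**Working it through.** The documents give no power, alpha, effect size or SD, so there is no figure of the plan's own to reproduce.

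**Inputs**
- 20 patients and 20 controls (section 10.1). The working below is for one group of 20.
- 10 participants per order: assumed, because section 5.2 gives no split.
- Five assessments (pretest, after set 1, after set 2, 20 min, 60 min): counted from the text of section 5.2. The design figure is not available.
- Independent errors of equal variance, and two-sided alpha 0.05: assumed.
- All effect sizes are assumed and shown as ranges.

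**Reading A: the repeated factor is time point**

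1. There are 20 × 5 = 100 observations. Participant and time use 20 + 4 = 24 parameters, leaving 76 error degrees of freedom.
2. Code set condition as +1 or −1 after set 1 and after set 2, with opposite signs in the two orders, and 0 elsewhere. The code sums to zero within every participant and at every time point. It is therefore orthogonal to the whole model, and all of its sum of squares (20 × 2 = 40) goes into the error.
3. With θ equal to half the condition difference in within-subject SD units, the expected error mean square is 1 + θ² × 40/76.

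| Condition difference | θ | 1 + θ² × 40/76 |
|---|---|---|
| 0.5 SD | 0.25 | 1.03 |
| 1.0 SD | 0.50 | 1.13 |
| 1.5 SD | 0.75 | 1.30 |

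4. An order difference that is the same at every assessment is absorbed by the participant term. Adding it leaves the rank at 24, and simulation with a 2 SD order difference gave an error mean square of 1.00. Only order differences that change across assessments reach this error.
5. For a single change score, pretest to after set 1, pooled over both orders, the variance is 1 + d²/4, where d is the order difference in SD of the change. For d = 0.5, 0.8 and 1.0 this is 1.0625, 1.16 and 1.25, a rise of 6%, 16% and 25%.
6. To put those d values on the ANOVA scale: under independent errors the variance of a change is twice the within-subject variance, so d² becomes 2d².
   - Orders differ only after set 1: the sum of squares is 20 × (2d²/4) × (1 − 1/5) = 8d², and 8d²/76 gives 3%, 7% and 11%.
   - The difference reverses after set 2: it is 20 × 2 × (2d²/4) = 20d², and 20d²/76 gives 7%, 17% and 26%.

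**Reading B: the repeated factor is set condition**

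A period shift p adds +p to the paired difference in one order and −p in the other. With 10 per order it cancels in the mean (simulated mean 0.66 for a true 0.66). It multiplies the SD of the paired differences by √(1 + p² × 20/19). Power starts at 80%, for a condition difference of 0.66 SD of the paired differences and n = 20.

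| Period shift p | SD multiplier | Power |
|---|---|---|
| 0.25 | 1.03 | 78% |
| 0.50 | 1.12 | 71–73% |
| 0.75 | 1.26 | 61% |
| 1.00 | 1.43 | 50% |

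**With the terms added.** Order × assessment adds 4 parameters (24 to 28), leaving 100 − 28 = 72 error degrees of freedom. Adding set condition after that keeps the rank at 28, so the contrast already lies inside the model. The error mean square returns to 1.00.

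**The case against.** The strongest reply is that no stated objective compares the two set types. The Study Summary describes a single-intervention pre-post design, and section 1.1 asks whether vibration improves voice. For that question, balanced order protects the average without any order term. Section 15.1 also defers to a cited acoustic study, and the design figure is not available, so the accurate statement is that the model names no such term.

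Most of this stands, and it limits the harm. A reader might infer that leaving out order biases the pre-post result. With balanced order it does not. A reader might also infer that any order difference inflates the error. A constant one does not.

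The reply does not dispose of the point. Section 5.2 takes the trouble to counterbalance the sets and to assess voice after each. The two set types resemble the two operating modes in section 4.1 (continuous vibration, and vibration only during detected speech), and section 1.1 looks ahead to a trial on dosage and duration. The text also favours the time-point reading: the final assessments are labelled by time, and section 5.3 says the repeated assessments serve to track change over time.

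**Conclusion.** The point holds as a matter of precision and of a missing contrast. It is a cheap improvement and does not threaten the validity of the average pre-post change. On the likelier time-point reading, the set contrast is not estimated and the five-assessment error mean square rises by roughly 3% to 30% over the range in the first table. On the other reading, the loss depends on the period shift. Both rest on the assumed 10/10 split, the five assessments, independent errors and the chosen effect sizes.

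Three stronger conclusions are tempting and not supported:

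- **The condition effect cannot be estimated at all.** This is true only on the time-point reading.
- **The omission amounts to discarding patients throughout.** The effective sizes 20/1.0625 = 18.8, 20/1.16 = 17.2 and 20/1.25 = 16.0 belong to one pooled change score. By the end of set 2 everyone has had both conditions, so they need not apply to later assessments.
- **Unequal order splits shift the patient–control difference.** Nothing in the documents indicates such an imbalance, and the voice model names no patient–control contrast.

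**What to change.** In section 15.1, define *assessment conditions* as the assessment time points, and add order (two levels, between participants) and order × assessment to the voice model. Report the between-order comparison after set 1 as the condition contrast. The sets are 5 minutes apart while effects are followed to 60 minutes, so later contrasts may contain carry-over that an order term cannot separate.

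In section 5.2, balance order within patients and within controls, and record each participant's order. No passage says it is recorded, and the remote file names carry only the subject ID and session number.

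The cost is one or two sentences in each section and about four error degrees of freedom (76 to 72 for 20 participants and five assessments). The comparison after set 1 is between participants and will be imprecise: with 10 per order in one group its standard error is √(1/10 + 1/10) = 0.45 SD of the change. It should be presented as an estimate with a confidence interval.
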